4.0 INCLUSION/EXCLUSION CRITERIA

INCLUSION	EXCLUSION
First time AF ablation with radiofrequency or cryo ablation	Planned surgical or hybrid (surgical + catheter) ablation
Repeat AF ablation if the patient has persistent AF and ablation of non-pulmonary vein substrate is planned (e.g. posterior wall ablation, mitral or roof line, etc)	Current use of amiodarone or within past 3 months
Able to provide written, informed consent	Use of oral steroids or colchicine
22 years of age or older	Pro-inflammatory, rheumatologic disorder (e.g. RA, SLE, IBD, psoriasis, ankylosing spondylitis)
	NYHA Class III/IV Heart Failure
	Active ischemia
	Hypertrophic Cardiomyopathy
	Cardiac or thoracic surgery within 6 months
	Expected life span < 1 year
	Creatinine clearance <30 ml/min
	Prior or planned heart transplantation
	Pregnant women
	Aspirin allergy
	Current use of MAO-I

RA=rheumatoid arthritis; SLE=systemic lupus erythematosus; IBD=inflammatory bowel disease (Crohn's, Ulcerative Colitis); NYHA=New York Heart Association; LVEF=left ventricular ejection fraction

Table 3: Eligibility Criteria.

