5.0 ENROLLMENT AND RANDOMIZATION

Recruitment and informed consent: Eligible subjects will be identified through EPIC. A member of the study team will request an introduction from the clinical staff. If the patient agrees, a member of the study team will approach the patient in person in Arrhythmia Clinic or by phone prior to AF ablation. Information describing the study, why the research is being done and what will be learned will be provided. The risks as described in this protocol will be delineated. The benefits will be described as general scientific knowledge, along with potential treatment advances. No direct immediate benefit to the subjects is anticipated. Informed consent will be documented with the subject's signature using an IRB-approved consent form for this protocol. An option will be available for phone consent with electronic signature.

Randomization: This will be a double-blind, randomized study. Eligible subjects will be randomized according to a stratified permuted block scheme with a block size of 8. This ensures that the cumulative number of assignments to each treatment (2-HOBA or placebo) will be in balance after each block of assignments had been made. Stratification will be made based on: 1) the planned ablation technique, cyroballoon vs. radiofrequency, 2) paroxysmal vs. persistent atrial fibrillation, 3) *de novo* vs. repeat ablation. A statistician will design the randomization table and enable the randomization tool within REDCap. After a patient enrolls for the study, the study nurse will determine the treatment assignment using the randomization tool in REDCap.

The study drug will be started 3 days prior to ablation. The dose of 2-HOBA will be 750mg three times per day (TID). At least 24 hours in advance, the study nurse will notify IDS to randomize the participant and prepare the study drug. MTI will provide 2-HOBA to the IDS as a 250 mg capsule. MTI will also provide matching

placebo capsules. The study nurse will arrange for the study drug to be given to the participant in-person or mailed. The total duration of the study drug is 31 days (3 days before ablation + 28 days after ablation).

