Sample size and power (Aim 1): The sample size of this study is based on a logistic regression of the binary primary endpoint of early AF recurrence by the end of follow-up. A total sample size of 162 with 81 in each arm will provide 81% power to detect a reduction in the rate of early recurrence of AF if the event rate is 29% in the treatment arm. This change corresponds to an odds ratio of 0.4 (treatment vs control), which is nearly equivalent to the odds ratio observed in similar trials using colchicine (colchicine OR 0.38)²⁶ at the significance level of 0.046 using a 1-sided Farrington and Manning likelihood score test, and a 48% rate of early recurrence in the placebo (control) group. The estimate 48% rate of early recurrence was extrapolated from our pilot data, which found a 45% rate of recurrence, but did not utilize continuous monitoring as will be performed in our trial. An interim analysis will be performed for superiority after half of the patients (n=40 per group) have completed their 28-day assessment of the primary endpoint at the significance level of 0.006. The final analysis will be performed after all patients have completed their 28-day assessment of the primary point at two-sided significance level of 0.041. Efficacy will be declared early at the interim analysis if the efficacy boundary is crossed ($p < 0.007$). All on-study patients will be followed for efficacy and safety until the planned end-of-follow-up. If the interim analysis indicates that the treatment is not better than the control by 13% (non-binding futility boundary $p > 0.4$), we may close the recruitment into study with regard to any recommendations of DSMB. The O'Brien-Fleming boundaries was used for the alpha- and beta-spending functions to preserve the overall Type I and Type II error.

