Primary Analysis (Aim 1): All FAS will be included in the primary analysis of AF recurrence, the primary efficacy endpoint. Binary recurrence of AF will be compared between treatment and control using a chi-square test. The primary analysis will be performed using a multivariable logistic regression model, where the dependent/outcome variable is the early AF recurrence (yes/no) by the end of the 28-day follow-up and the primary independent/predictor variable is the treatment arm (2-HOBA or placebo). Adjustment will be made for age, gender, AF type (paroxysmal versus persistent), method for pulmonary vein isolation (radiofrequency versus cryoablation), additional ablation lesions (yes/no), BMI (continuous), and hours of monitoring (0-672 hours). To avoid over-fitting our multivariable logistic regression model, a 10:1 ratio for degrees of freedom per the less frequent outcome event will be used in our modeling. Nonlinear form of the continuous predictors (age, BMI, and hours of monitoring) will be considered when building the model with restricted cubic splines. Models will be evaluated for goodness-of-fit, and internally validated for the calibration and discrimination performance using the bootstrap method.

Secondary Analysis (Aim 1): A secondary analysis will analyze a surrogate of AF burden as the endpoint and designed to account for the impact of cardioversion on AF burden assessment. AF burden is the percentage of time in AF, atrial tachycardia, or atrial flutter over total time monitored. The secondary analysis will use the data

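### The primary logistic model is given two rules that conflict at the plan's own event rates: a fixed list needing 8 degrees of freedom and a 10:1 cap that allows 6, with nothing saying which prevails

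*Combined protocol and SAP*

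**What the plan says.** All of the following is in section 10.1 unless stated.

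- **The list.** The primary analysis is a multivariable logistic regression of 28-day recurrence on treatment arm. "Adjustment will be made for age, gender, AF type (paroxysmal versus persistent") opens the covariate list. Method of pulmonary vein isolation follows, and the list ends with "additional ablation lesions (yes/no), BMI (continuous), and hours of monitoring (0-672 hours"). That makes seven covariates besides treatment.
- **The cap.** To avoid over-fitting, "a 10:1 ratio for degrees of freedom per the less frequent outcome event will be used in our modeling". Read literally the ratio is the wrong way round. The only workable meaning is ten of the less frequent outcome per df, and I use that.
- **Splines.** Nonlinear forms of age, BMI and hours of monitoring "will be considered when building the model with restricted cubic splines". No number of knots and no criterion are given.
- **A second test.** The same paragraph also states: "Binary recurrence of AF will be compared between treatment and control using a chi-square test".
- **The level.** The sample-size paragraph sets the final analysis "at two-sided significance level of 0.041".
- **Strata.** Section 5.0 stratifies randomisation by planned technique, AF type and "3) *de novo* vs. repeat ablation". The third factor is not in the model.
- **Hours.** The secondary analyses include adjustment for duration of smartwatch use, although hours of monitoring (28 x 24 = 672) is already a primary covariate. The plan does not say how the two differ.

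**The concern.** Both the list and the cap are worded as commitments, and at the design rates they cannot both be kept. An analyst who fits the list breaks the cap; one who obeys the cap must drop or merge terms with no guidance on which. The size the cap permits is known only once recurrences have been counted, so the confirmatory model is not settled until outcome data are in. Splines add further choices.

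This is the test on which efficacy will be declared. If two models that both fit some reading of the paragraph give p-values on either side of 0.041, a reader cannot tell which is the planned one. The same question arises at the interim, because the sample-size paragraph does not say whether the adjusted model is used there.

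**Working it through.** **Inputs** (section 10.1, sample size): 81 per arm, 162 in total; recurrence 48% on placebo and 29% on 2-HOBA. The plan states no event total and no df count. Its one figure from these inputs is 81% power at one-sided 0.046; a normal-approximation calculation gives 79.3%, close enough to confirm that these are the design inputs.

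**Size of the listed model.** Treatment 1 + age 1 + sex 1 + AF type 1 + method 1 + additional lesions 1 + BMI 1 + hours 1 = 8 df, all linear. A restricted cubic spline with k knots adds k - 2 df per continuous predictor. With all three splined, df = 8 + 3(k - 2), which is 11, 14 or 17 for 3, 4 or 5 knots.

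**Size the cap allows.** Expected events = 81 x 0.48 + 81 x 0.29 = 62.4, and non-events = 162 - 62.4 = 99.6. The less frequent outcome is 62.4; 62.4/10, rounded down, is 6 df. The 8-df list has 62.4/8 = 7.8 events per df.

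**Sensitivity to the rates**

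| Rates (placebo/2-HOBA) | Expected events | Cap |
|---|---|---|
| 48%/29% | 62.4 | 6 df |
| 48%/27% (odds ratio exactly 0.4) | 60.7 | 6 df |
| 45% (pilot)/29% | 59.9 | 5 df |
| 48%/48% | 77.8 | 7 df |

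**Chance of each cap.** This is the exact distribution of the sum of two binomials (n = 81 each), with the less frequent outcome divided by 10 and rounded down.

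| Cap | 48%/29% | 48%/48% |
|---|---|---|
| 4 df | 1.6% | 0% |
| 5 df | 30.4% | 0.2% |
| 6 df | 55.9% | 10.5% |
| 7 df | 11.8% | 72.9% |
| 8 df | 0.2% | 16.4% |

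The less frequent of two outcomes among 162 people is at most 81, so the cap never exceeds 8 df. The full list plus a single spline term (at least 9 df, needing 90) can never satisfy it.

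**At the interim**, if the adjusted model is used: 40 x (0.48 + 0.29) = 30.8 events, so 3 df.

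**What the open choice does.** These are simulations with 162 participants, Wald tests at two-sided 0.041 and assumed covariate odds ratios between 1 and 1.5. Each figure is the share of trials in which the two models disagree on significance.

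- At the design effect: two models that each keep treatment and five of the seven covariates (6 df), 3.8% to 7.0%; such a model against the 8-df list, 3.1% to 5.8%; the 8-df list against its 17-df spline version, 6.4% to 7.2%.
- Under no effect, with each trial using the model size its own event count permits: 0.8% to 1.7%. The linear list against its 17-df version: 2.2% to 2.6%.

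**Models fixed in advance.** Null rejection (nominal 4.1%) is 3.7% to 4.9% for the 8-df linear list and 4.8% to 5.4% for the 17-df version.

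**The missing stratum.** Adding de novo versus repeat changes the decision in 1.1% to 2.1% of trials at the design effect (assuming 20% repeat procedures, with odds ratio 1 to 2.5).

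**Hours of monitoring.** Assume no drug effect on recurrence and a 0.3 SD shift in hours between arms, in either direction. If recurrence itself moves hours by 0.5 SD, the hours-adjusted odds ratio is 0.86 or 1.16 and the unadjusted one is 1.00. If hours drives detection (log-odds 0.5 per SD), the unadjusted odds ratio is 1.16 or 0.86 and the adjusted one is 1.00 to 1.01. With a 0.1 SD shift, rejection stays at 3.8% to 4.3% in every case.

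**The case against.** The best defence is that the wording already ranks the instructions. Adjustment for the seven covariates is firm, whereas nonlinear forms are only to be considered, so the natural default is the 8-df linear model with the cap restraining splines. This narrows the ambiguity but does not remove it: the linear list alone exceeds 6 df, and leaving treatment out of the count still gives 7 against 6. The cap is also worded as a commitment, and no other part of section 10 gives a priority, a dropping order or a date for fixing the model.

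Four stronger readings are tempting, and the documents do not support them.

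- *The 8-df model is over-fitted and invalid.* Ten per df is the plan's own rule of thumb. At 7.8 events per df the fixed linear model rejects at close to its nominal rate.
- *The list always breaks the cap.* It fits when there are 80 to 82 events, which has a 16% chance at 48%/48%.
- *The team will choose the most favourable model, so type I error is inflated.* No passage describes such a practice.
- *Omitting the repeat-ablation stratum, or including hours, biases the result.* Section 4.0 admits a "Repeat AF ablation if the patient has persistent AF and ablation of non-pulmonary vein substrate is planned", so AF type and additional lesions partly carry that stratum. Hours can mislead whether included or left out, and the documents do not show which mechanism operates.

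It is also fair that every disagreement percentage rests on assumed covariate effects.

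**Conclusion.** The concern stands as a conflict between two stated rules for the confirmatory test. At the design rates the listed model and the cap differ by 2 df, both can be met in 0.2% of trials, and the model the cap permits depends on the observed event count. That part follows from the plan's own inputs and is certain.

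The consequence is moderate and less certain: a changed decision in several percent of trials at the design effect and in about 1% to 2% under no effect (up to 2.6% for the widest spline comparison), given covariate odds ratios of 1 to 1.5. The missing stratification factor is a smaller, partly mitigated gap. The place of hours of monitoring, a post-randomisation variable, needs settling in the same revision. This should be fixed, but it does not undermine the design.

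**What to change.** Before any unblinding, including the interim, name one primary logistic model with linear terms:

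1. treatment;
2. the three stratification factors as randomised: planned technique, AF type, and de novo versus repeat;
3. a fixed list of covariates known at baseline, such as age, sex, BMI, and additional lesions as planned rather than as delivered.

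State that this model is used whatever the event count, that the 10:1 rule and splines apply only to secondary or exploratory models, and that its treatment term is the confirmatory test with the chi-square test supportive. Say whether the interim uses the same model.

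Because hours of monitoring is measured after randomisation, keep it out of the confirmatory model. Report the hours-adjusted result as a sensitivity analysis, merged with the smartwatch-duration analysis already listed among the secondary analyses.

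The cost is SAP wording only. Linear terms may fit slightly worse than splines. In simulation, a fixed model with treatment, the three strata, age, sex, BMI and additional lesions, without hours, had null rejection of 4.3% to 4.9% and power within 0.9 points of the listed 8-df model. An ordered, outcome-blind rule for removing terms would also resolve the conflict, but the model would still vary with the event count.

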recurrence of AF. In the presence of 2-HOBA, IsoLG will preferentially bind to and therefore be inactivated by 2-HOBA thereby sparing injury to the atrial tissue caused by oxidative stress and its contribution to early recurrence of AF. Early recurrence of AF will be measured by ECGs that are recorded once per day by a smartwatch (Apple Watch, Apple Inc., Cupertino, CA) with additional ECGs recorded by the participant if they experience symptoms of AF, or if the smartwatch alerts the participant of a possible AF episode via its auto-detection AF monitoring algorithm. The Apple Watch's AF algorithm is based on sampling of heart rate and variability and will give an audible alarm if those parameters indicate a possible episode of AF. The smartwatch records a single-lead ECG if the participant touches the watch with their contralateral hand. The day and time of the episode is also stored by the smartwatch. At the end of the 28-day follow-up period, study personnel will review the stored ECGs. Blood will be drawn prior to ablation and on post-procedure Day 1 for measurement of IsoLG-adduct levels. DNA will be extracted to explore a pharmacogenomic interaction with haplotypes at the chromosome 4q25 AF risk locus, which: 1) is strongly associated with the development of AF and the early recurrence of AF after ablation²⁷; and 2) has been reported to be a regulator of an anti-oxidant gene program in response to cardiac injury.²⁸

The proposed double-blind, randomized, placebo-controlled trial of 2-HOBA in patients undergoing AF ablation is designed to address the following Specific Aims:

Specific Aim 1: To test the hypothesis that treatment with 2-HOBA reduces early recurrence of AF (clinical endpoint)

Specific Aim 2: To test the hypothesis that treatment with 2-HOBA reduces circulating levels of IsoLG-adducts (biochemical endpoint)

Specific Aim 3: To explore the idea that genetic variation at the 4q25 (*PITX2*) AF susceptibility locus modulates the clinical and biochemical response to 2-HOBA

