Table 2. Summary of reported adverse events by dose in multi-dose Phase 1 study of 2-HOBA

The pharmacokinetics observed in the multi-dose trial largely resembled those obtained in the single dose study. 2-HOBA had a T_{max} of 1-2 h and achieved steady-state C_{max} in the range of those observed with the highest dose in the single dose study - 3177 ± 1993 ng/mL after 15 days of dosing at 500 mg and 2292 ± 913 ng/mL after 15 days of dosing at 750 mg. Both groups (500 and 750 mg doses) experienced progressive AUC increases over the 15 days, yielding accumulation ratios of 1.25-1.50. The half-life in this dosing interval was slightly longer than that observed in the single dose study, contributing to the increased accumulation of 2-HOBA. Average systemic exposure (AUC and C_{max}) was similar for the 500 and 750 mg doses. Response to 2-HOBA revealed considerable variability among subjects, as those dosed at the 500 mg regimen showed greater exposure on average than volunteers dosed at 750 mg. Oral bioavailability is not currently established in humans, and limits the interpretation of these data. Notably, the major metabolite of 2-HOBA, salicylic acid, showed a peak plasma

concentration of 12.8 ± 3.7 mg/L, considerably lower than the accepted therapeutic range of 150-300 mg/L required for anti-inflammatory activity. Consequently, inhibition of cyclooxygenases was not observed, as determined by urinary metabolites of 3 major prostaglandins, pGE-M, TxB₂-M, and PGI-M.]

No evaluation of the compound in pediatric settings or in patients with reported history of disease has been undertaken. A greater range of age and ethnicity should be explored in additional clinical studies to gain a better understanding of its clinical profile.

3.3. The peak plasma concentration of 2-HOBA in humans will reach the level demonstrated to reduce IsoLG-adduct formation in experimental models

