6.0 STUDY PROCEDURES

Encounter 1: Enrollment and Informed Consent

- Performed by a member of the study team either in person in the Vanderbilt Arrhythmia Clinic or by phone with an electronic signature.
- In person meetings will occur in either: 1) the Vanderbilt Cardiac MRI Suite (if a pre-ablation cardiac MRI is scheduled), 2) the Vanderbilt Cardiac CT Suite (if a pre-ablation cardiac CT is scheduled), 3) the VHVI Research Room (5th Floor Medical Center East, South Tower), or at their cardiology or imaging appointments at the One Hundred Oaks location (if applicable).
- A supply of the study drug will be given to the participant along with dosing instructions either in-person or via the mail.

Encounter 2: Day of ablation

- The participant will arrive the morning of ablation as instructed by the clinical team
- Prior to ablation, the participant will be taken to the EP pre-op holding room. A dose of the study drug will be taken at this time (~30 minutes prior to the procedure).
- The study team will provide the participant with the smartwatch as well as an accompanying smart phone (if the patient does not own their own iPhone). The study team will initialize the smartwatch and phone with configurations to collect data, and instruct patients on how to record ECGs from the smartwatch.
- After the patient arrives in the operating room, they will undergo standard of care preparation for surgery including sterile drape and administration of general anesthesia using endotracheal intubation and mechanical ventilation. Central venous catheters are placed in the femoral veins as part of the procedure.
- A 30 mL blood sample will be collected from one of the central venous catheters prior to ablation. 10 mL of blood (divided between purple and blue top tubes) will be delivered to the Core Laboratory for Cardiovascular Translational and Clinical Research, and 20 mL will be put in green top tubes, placed on ice, and delivered to the research laboratory for culturing of monocytes and dendritic cells for measurement of isolevuglandin-adduct levels.
- AF ablation will then be performed as per standard of care by the primary operator and clinical team.

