provided by the continuous HR monitor provided by the smartwatch. The analysis will be performed using a linear mixed models (LMM) in which the AF burden is assessed weekly during the 4-week (28-day) follow-up period. Same covariates mentioned in the primary analysis will be considered. Additionally, AF burden will also be analyzed in ordinal scale using generalized estimating equation (GEE), ranked based on severity according to increasing AF burden and whether or not a cardioversion was performed. For any missing data in the covariates, we will use a multiple imputation method that incorporates predictive mean matching and flexible additive imputation models as implemented in the aregImpute function in the *Hmisc* R package. The impact of missing data on the validity of results will be examined with a pattern-mixture approach using the R package *SensMice*. This will be done for Aims 1 and 2. Additional secondary analyses will include: 1) multivariable modeling of participants who were excluded from the primary analysis due to the use of colchicine or steroids during the follow-up period (will examine clinical and biochemical endpoints); 2) multivariable modeling with adjustment for 2-HOBA levels for the clinical and biochemical endpoints; 3) multivariable modeling with adjustment for duration of smartwatch use.

Interim Analyses (Aim 1): An interim analysis will be performed by the study team and reviewed by the DSMB. When 50% of the target enrollment is reached testing for an association between 2-HOBA or placebo and significant adverse events (see Ethical Aspects of the Proposed Research for details), superiority and futility will be performed (see above: Sample Size and Power Aim 1). The interim analysis will include early stopping rules for superiority, futility, and harm.

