10.2. Aim 2 (Biochemical Endpoint)

Primary hypothesis: The primary endpoint for Aim 2 will be the IsoLG-adduct content of dendritic cells expressed as a percentage (IsoLG-adducted dendritic cells/total dendritic cells x 100). We will test the hypothesis that 2-HOBA reduces the change in IsoLG-adduct levels that occurs with AF ablation (as measured on post-procedure day #1 minus pre-ablation blood samples).

Sample size and power (Aim 2): Our pilot data shows that the change in dendritic cell IsoLG-adduct level is 23% following ablation in our placebo (control) group and we expect the range of possible observed reduction to be 20-40%. With n=81 participants in each arm, the study provides at least 80% power to detect a minimal 22% reduction in IsoLG-adduct level at two-sided significance level of 5%.

Primary Analysis (Aim 2): Our primary analysis will use multivariable linear regression to test whether our primary determinant (2-HOBA versus placebo), significantly reduces the change in IsoLG-adduct levels (continuous), adjusted for baseline pre-ablation IsoLG-adduct level and other potential confounding factors: age, sex, method for pulmonary vein isolation (radiofrequency versus cryo), additional ablation lesions (yes/no), and BMI (continuous). The IsoLG content of dendritic cells adjusted for baseline level will be presented for both treatment arms, together with corresponding 95% confidence intervals (CIs) and p-values will be graphically interpreted using boxplots, partial effect plots, residual plots, etc.

Secondary Analysis (Aim 2): A secondary endpoint will be the IsoLG-adduct level in monocytes. Due to the prohibitively labor-intensive process required to measure IsoLG content in dendritic cells and monocytes, only the pre-ablation and post-procedure day#1 samples will be analyzed for the analysis. However, blood samples from 2 additional time points (baseline and post-procedure day #28) will be available for pharmacokinetic

analysis and secondary analysis of other serological markers. These will include malondialdehyde and other biomarkers of oxidative stress.

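### A secondary model adjusts the arm comparison for 2-HOBA level, a consequence of assignment and the drug's own route of action, so its arm term is not the randomised treatment effect

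*Combined protocol and SAP*

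**What the plan says.** Section 10.1, under the secondary analysis for Aim 1, ends with three further analyses. The second is "multivariable modeling with adjustment for 2-HOBA levels for the clinical and biochemical endpoints". It stands next to a third item that adjusts for duration of smartwatch use.

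The models that would be adjusted are built on randomised arm. For Aim 1 the "primary independent/predictor variable is the treatment arm (2-HOBA or placebo"; for Aim 2 the regression is to "test whether our primary determinant (2-HOBA versus placebo), significantly reduces the change in IsoLG-adduct levels (continuous".

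Section 2.0 gives the mechanism: "IsoLG will preferentially bind to and therefore be inactivated by 2-HOBA".

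On timing, section 5.0 says "The study drug will be started 3 days prior to ablation". The first blood draw listed in section 6.0 is on the day of ablation: "A 30 mL blood sample will be collected from one of the central venous catheters prior to ablation". Section 10.2 says that "blood samples from 2 additional time points (baseline and post-procedure day #28) will be available for pharmacokinetic" work.

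The plan does not say which sample supplies the level, how placebo patients are coded, whether the item is confined to the active arm, or how the arm coefficient would be read.

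**The concern.** A covariate that is caused by treatment and carries its effect should not be held fixed when the treatment effect is estimated. With placebo levels near zero, only the active arm informs the level slope. The arm coefficient is then the active-arm prediction at a level near zero minus the placebo result, and few if any treated patients sit there. The slope itself compares patients who differ in absorption, adherence, body size and renal function, so randomisation does not protect it.

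At stake is a prespecified result for both endpoints that could be reported as the treatment effect after adjustment. It could make a working drug look ineffective, or give an inert drug an apparent effect.

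**Working it through.** **The plan's own figure.** Section 10.1 states 81% power for 81 per arm, 48% against 29%, one-sided 0.046.

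- Null SE = √(2 × 0.385 × 0.615 / 81) = 0.0765.
- Alternative SE = √((0.48 × 0.52 + 0.29 × 0.71) / 81) = 0.0750.
- One-sided 0.046: Φ[(0.19 − 1.685 × 0.0765) / 0.0750] = 79.3%. A two-stage calculation with the interim gives 80.4%. The stated figure is reproduced within 2 points.
- Two-sided 0.041, the level stated for the final test: Φ[(0.19 − 2.044 × 0.0765) / 0.0750] = 67.4%.

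The second value is the reference below. The gap between the two is a separate matter.

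**Collinearity of arm and level.** Inputs are the steady-state peak levels in section 3.2: "2292 ± 913 ng/mL after 15 days of dosing at 750 mg" (CV 0.40), and 3177 ± 1993 ng/mL at 500 mg (CV 0.63). The latter is not this trial's dose and serves only as a high-variability bound. With 1:1 allocation and placebo level zero (assumed):

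- R² = mean² / (mean² + 2 × SD²), and VIF = 1 + mean² / (2 × SD²).
- CV 0.40: VIF = 1 + 2292² / (2 × 913²) = 4.15; R² = 0.76; SE × √4.15 = 2.04.
- CV 0.63: VIF = 1 + 3177² / (2 × 1993²) = 2.27; R² = 0.56; SE × √2.27 = 1.51.
- Level zero lies 2292/913 = 2.5 SD, or 3177/1993 = 1.6 SD, below the active-arm mean.

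The VIF is a linear-model result. In simulated logistic fits with an inert drug, the arm SE went from 0.32 to 0.67 (CV 0.40) and from 0.32 to 0.49 (CV 0.63), which agrees.

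**Effect on the arm term.** Simulated logistic regression, 81 per arm, 48% against 29%, placebo level zero, other covariates omitted, Wald test at two-sided 0.041. Ranges cover the two CVs and, for the saturating row, two curves.

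| Assumed shape of the drug effect | Arm OR without level | Arm OR with level | Chance arm shows benefit, without level | Chance arm shows benefit, with level |
|---|---|---|---|---|
| Linear in level, wholly through level | 0.44 | about 1.0 | 67-71% | 1-2% |
| Saturating, wholly through level | 0.44 | 0.55-0.68 | 67-71% | 9-16% |
| Equal at every level | 0.44 | 0.44 | 67-71% | 18-32% |

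The saturating curve is x / (x + c), with x the level divided by its mean. Here c = 2.7/8.5 = 0.32, from the concentrations in section 3.3, or c = 1. A repeat run with gamma-distributed levels gave 7-18% for that row, so it should be read to within a few points. In the linear row, 1-2% is about the test's false-positive rate in that direction (0.041/2 = 2.05%).

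**Loss of randomisation.** Take an inert drug and an unmeasured factor tied to both level and AF risk (assumed correlation 0.6 with level and log-OR 0.6 per SD). The arm OR without level is 1.00. With level it becomes 0.43-0.58 or 1.71-2.39, depending on the factor's direction, and two-sided false rejection is 16-21% against a nominal 4.1%.

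No simulation was run for the biochemical endpoint. The VIF argument applies there directly, because that model is linear.

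**The case against.** The text is one clause. It does not say that arm stays in the model, and it may be a loosely worded exposure-response analysis. That is possible, but the word adjustment and the neighbouring smartwatch item favour the covariate reading. If arm were dropped, the model would still be non-randomised and would need that label. That placebo levels are near zero is likewise an inference, though small non-zero levels would not change the conclusion.

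A reader might infer that this model will show no effect whenever the drug works through exposure. The documents do not support that. An arm OR near 1.0 follows only if the log-odds fall linearly with level and the whole effect runs through it. Section 3.3 points rather towards saturation: about 2.7 μM sufficed in mice, against 8.5 μM expected at 550 mg. The arm OR is then 0.55-0.68, and it does not move at all if the effect is the same at every level. The loss of power remains in each case.

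A reader might also infer that the trial's main result is compromised. It is not: the primary models in sections 10.1 and 10.2 contain arm without drug level, and this item carries no alpha, sample size or stopping rule. Section 10.1 also calls Aim 2 exploratory.

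It would be too strong to say that no treated patient has a level near zero. The full analysis set keeps everyone randomised, so active-arm patients who did not take the drug may be there. Finally, the Phase I inputs are thin: peak levels from six active healthy volunteers per dose, whereas the trial samples are not timed to the peak.

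**Conclusion.** The concern holds for this secondary item. On the plain reading, neither the arm coefficient nor the level slope estimates the randomised effect of 2-HOBA, whatever the shape of the exposure-response curve. That conclusion rests on level being produced by assignment and lying on the protocol's stated causal path, and needs no simulation.

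The size does depend on assumptions: trial levels that vary like the Phase I peaks, placebo near zero, and a chosen effect shape. On these, the arm SE grows about 2.0-fold (CV 0.40) or 1.5-fold (CV 0.63), and the chance of showing benefit drops to between about 1% and 32%. The odds ratios are scenarios, not predictions.

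The unspecified sampling time adds to the problem. A day-28 level is taken at the end of the outcome window, so a recurrence that changed drug-taking could alter the level. This should be corrected before unblinding, but it does not touch the primary conclusions.

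**What to change.** Replace the second additional analysis in section 10.1 with an exploratory exposure-response analysis within the 2-HOBA arm. Regress recurrence, and separately the change in IsoLG-adduct level, on measured 2-HOBA level with adjustment for baseline covariates, and label the result non-randomised.

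Name the sample: the pre-ablation draw on the day of ablation. It is on drug, precedes the outcome window and is already collected. Do not use the day-28 sample. Section 10.2 should then list the pre-ablation sample for the 2-HOBA assay, since it now names only baseline and day 28 for pharmacokinetics.

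State that no arm coefficient conditional on drug level will be reported as a treatment effect, and that the randomised effect is that of the primary models in sections 10.1 and 10.2.

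The cost is a sentence or two in the plan, with no new blood draw and no change to sample size or alpha. The slope will rest on the 81 active-arm patients only, but with placebo levels near zero they are the only patients who inform it in any model that includes arm. A prespecified causal mediation method would be an acceptable alternative, with stronger assumptions to state.
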